---

## **List of abbreviations**

BA – Bronchial asthma

RSAR – Russian severe asthma registry

SA - severe bronchial asthma

GINA - Global Initiative for asthma (Global Strategy for Asthma Management and Prevention)

eCRF - electronic case report form

ICS - inhaled glucocorticosteroids

LABA - long acting  $\beta$ -agonists

LAMA – long-acting antimuscarinic agents

COPD - chronic obstructive pulmonary disease

EDS - electronic data logging system

LLC "RSMI" - Limited Liability Company "Regional United System of Medical Informatization"

SNOMED CT - the dictionary of the systematized nomenclature of medical clinical terms

IHTSDO - organization for the development of international health terminology

RAACI - Russian Association of Allergology and Clinical Immunology

QMS - Quality Management System

SOP - standard operating procedure

NEC - National Ethics Committee

RRS - Russian Respiratory Society

CBD - The central database

IPF - idiopathic pulmonary fibrosis

EMC - emergency medical care

Treatment and prophylactic institution

ACQ-5 - Asthma Control Questionnaire (questionnaire for asthma control, 5-question version)

ACT - Asthma Control Test (Asthma Control Test)

OCS - oral corticosteroids

LTRA - a leukotriene receptor antagonist

## **RESPONSIBLE PARTIES**

1. Limited liability company "Regional United Medical Informatization System" (LLC "RSMI") within the framework of the project of the Russian Severe Asthma Registry (RSAR) takes responsibilities to develop and implement software for the work of physicians-investigators within the RSAR creating a database of patients with severe bronchial asthma (SA) on the territory of the Russian Federation on an already existing software company product, named "Medical online platform ROSMED.INFO" protected according to the current legislation of Russian Federation.
2. The limited liability company "Regional United Medical Informatization System" within the framework of the project RSAR assumes the responsibility to perform the functions of a personal data operator of physicians and patients participating in the study.
3. Limited liability company "Regional United Medical Informatization System" within the RSAR project assumes the responsibility for management and administration, including information and technical support, of the project during the whole period of the study.
4. NPO "Russian Respiratory Society" within the project of RSAR assumes the obligation to contribute to the development of indicators of the Electronic Database, to supervise the development of principles and parameters of patient questioning, to create reference materials for patients and/or their legal representatives, to supervise the development of CRF, repeat/monitoring visits and other clinical parameters, correlating with the issues of prophylaxis, management, dynamic clinical monitoring of the health status and rehabilitation process of patients with severe asthma, but not limited to these areas of activity.
5. Russian Association of Allergology and Clinical Immunology (RAACI) within the project of RSAR assumes the obligation to contribute to the development of indicators of the Electronic Database, to supervise the development of principles and parameters of patient questioning, to create reference materials for patients and/or their legal representatives, to supervise the development of CRF, repeat/monitoring visits and other clinical parameters, correlating with the issues of prophylaxis, management, dynamic clinical monitoring of the health status and rehabilitation process of patients with severe asthma, but not limited to these areas of activity.

## **PROJECT DELIVERY COLLABORATORS**

LLC RSMI specializes in conducting medical observational non-interventional prospective multicenter studies.

LLC "RSMI" owns the patented Russian software product "Medical online platform ROSMED.INFO", which serves as a base for development and maintenance of observational studies (registries) on various nosologies, including severe asthma.

NPO "Russian Respiratory Society" (IPO "RRS") is a non-profit public organization that unites on a physician of various specialties engaged in the management of patients with various pulmonological diseases. Among the members of the NPO "RRS" there are leading Russian opinion leaders, the main freelance specialists of the Ministry of Health of the Russian Federation,

the main non-staff regional specialists in the field of respiratory / allergic diseases, who possess extensive experience in development and conductance of clinical trials. The activities of NPO RRS focus on the establishment of best practices and standards in pulmonology, aimed on improvement of the quality of research in real practice for all stakeholders, including patients, clinical practice specialists, representatives of the pharmacological industry and law enforcement / regulatory bodies.

## PROTOCOL SYNOPSIS

---

The Russian registry of patients with severe asthma to collect anonymous long-term evidence.

The Russian Severe Asthma Registry is a Russian initiative to collect anonymous long-term evidence for patients with severe asthma in Russia. The RSAR initiative is realized under the efforts of the Interregional Public Organization "Russian Respiratory Society" and LLC "RSMI" with the sponsorship of "AstraZeneca Pharmaceuticals" LLC.

The developed RSAR electronic database is a Russian software product that meets the current requirements of the Russian legislation in the field of working with personal data and the implementation of similar observational studies.

Participating researchers also agree to grant access and share anonymous data at the patient level as part of the work to implement the RSAR initiative. Participants will provide high-quality data for the development of data sets for research, approved by the Russian Respiratory Society (RPO), which has priority in owning and implementation in scientific field of the gained data. Based on ethical, legal and regulatory authorizations, anonymous data will be collected in the Central Database (CDB) on respiratory diseases (referred to here as the RSAR database) to create sets of important data and the necessary analysis. CDB is part of the software "Medical online platform ROSMED.INFO".

---

## MILESTONES

Period 01/2018 – 12/2018		
Invitation of physicians-investigators to the project, the initiation of the RSAR work	03/2018	
Project working group formation of curators, sponsors, medical experts		
Programming of the individual patient case report form (child (from 12 years) and adult versions)		
The beginning of filling in eCRF by the physicians-investigators	03/2018	
Project management, filling of eCRF by investigators	03/2018-12/2018	
Organization of the database and user's personal information protection	03/2018-12/2018	
Data base administration	03/2018-12/2018	
Data entry in CRF by investigators	03/2018-12/2018	
Analytic report	07/2018 and 12/2018	
Period 01/2019 – 12/2019		
Project management, filling of eCRF by investigators	01/2019-12/2019	
Organization of the database and user's personal information protection	01/2019-12/2019	
Data base administration	01/2019-12/2019	
Data entry in eCRF by investigators	01/2019-12/2019	
Analytic report	06/2019 and 12/2019	
Period 01/2020 – 12/2020		
Project management, filling of eCRF by investigators	01/2020-12/2020	
Organization of the database and user's personal information protection	01/2020-12/2020	
Data base administration	01/2020-12/2020	
Data entry in eCRF by investigators	01/2020-12/2020	
Analytic report	06/2020 and 12/2020	
Period 01/2021 – 12/2021		
Project management, filling of eCRF by investigators	01/2021-12/2021	

Organization of the database and user's personal information protection	01/2021-12/2021	
Data base administration	01/2021-12/2021	
Data entry in eCRF by investigators	01/2021-12/2021	
Analytic report	06/2021 and 12/2021	
Period 01/2022 – 12/2022		
Project management, filling of eCRF by investigators	01/2022-12/2022	
Organization of the database and user's personal information protection	01/2022-12/2022	
Data base administration	01/2022-12/2022	
Data entry in eCRF by investigators	01/2022-11/2022	
Analytic report	06/2022 and 12/2022	
	Total taking into account all receipts	

## 1.0. BACKGROUND & RATIONALE

### 1.1. BACKGROUND

#### Severe asthma

BA is a heterogeneous disease characterized by chronic inflammation of the upper respiratory tract. BA affects 5-15% of people worldwide and its prevalence has increased in the last decade [1]. Asthma management to achieve optimal control and prevention of exacerbations using a step approach in pharmacotherapy is detailed in national and international guidelines [2]. Nevertheless, the question of precise statistical data on the true incidence of severe asthma remains open. In the study "NIKA" [19], an assessment of the level of asthma control in 1,000 patients from 26 outpatient clinics in 12 cities of the Russian Federation was carried out. The level of control was assessed clinically and using specialized questionnaires ACQ-5 and ACT. As a reference method of assessment, the evaluation of symptoms and spirometry parameters were performed in accordance with the GINA criteria. In general, controlled BA was noted in 23% of patients, partial control and uncontrolled asthma - in 35% and 42%, respectively. When diagnosing the level of control, physicians made mistakes in 49% of cases. The use of the ACQ-5 and ACT tests produced a higher and approximately comparable quality of the control evaluation (64% and 60% of

adequate assessments), but the ACT had a systematic error in overestimating the level of control of asthma compared to the GINA criteria. Despite the availability and use of preventive treatment, the costs associated with asthma are increasing, and affect both individuals and health facilities. Regardless of the improved understanding of the nature of the disease, the factors that affect the loss of control are still unclear and largely remain hypothetical. Part of the difficulties lies in determining the severity of asthma, assessing its symptoms and their intensity.

The program of the study of severe asthma revealed various subgroups of severe asthma on the basis of changing clinical manifestations, pathophysiological mechanisms and biomarkers [4]. In this study, 438 patients with asthma were studied. The authors found that patients with severe asthma tend to be older with a longer illness, daytime symptoms, intensive use of emergency therapy, sinusitis and pneumonia. Despite the fact that lung function was reduced in these patients, most patients had reversibility of bronchial obstruction after taking the bronchodilator [4]. A better understanding of the mechanisms of BA should make an obvious improve in patients' management.

### **Biomarkers and phenotypes in SA management prognosis of treatment response.**

Patients with BA of mild to moderate severity can control symptoms with increasing doses of inhaled glucocorticosteroids (ICS) in combination with long-acting  $\beta$ -agonists (LABA) or leukotriene antagonists. In patients with more severe asthma and frequent exacerbations, this treatment may not be sufficient to control symptoms and prevent exacerbations. Despite the growing range of medicines and improved design of inhalers and patient care, deaths continue to increase due to asthma, with an increase of 17% between 2014 and 2015 only in Great Britain [6]. The novel methods of treatment can help to fight this tendency. However, new therapies are often expensive, and there is a need to identify patients who can get the most benefit from such treatment.

Biomarkers assessment now is an important tool used to achieve optimal management of patients with BA, especially, SA. Biomarkers can be used to study the function of organs or other health parameters [7], providing information on the severity of the disease and the predicted outcomes of treatment, as well as on choosing the most effective treatment for particular patients.

For example, patients with severe BA and significant eosinophilia have a greater risk of exacerbating [8]. Eosinophils can affect the mucous of the upper respiratory tract, provoking epithelial damage and changes in the structure of the upper respiratory tract in asthma, thus affecting the severity of the disease. Studies have shown that peripheral blood eosinophilia can be used as a biomarker to predict the effectiveness of anti-IL-5 therapy in the prevention of exacerbations [9, 10, 11]. Recent data suggest that other variables, as like eosinophils, can predict asthma exacerbations. These include local eosinophilia, as well as nasal polyps and concomitant diseases, including diabetes mellitus [12].

Like the number of eosinophils, an increase in the exhaled nitric oxide fraction (FeNO) helps to predict the exacerbations of asthma (13). An increase in FeNO is considered a clinical biomarker of inflammation. Nevertheless, the values of FeNO are affected by many associated

factors, including tobacco smoking, obesity and the use of glucocorticosteroids [7]. There is a need for a better understanding of when FeNO plays the role of a biomarker in BA. In particular, a combination of data on FeNO and eosinophils of blood can help in predicting who will benefit greatly from the biological therapy. Moreover, a significant proportion of patients with asthma also have an allergic sensitization. The presence of allergen-specific IgE along with exposure to the allergen are known risk factors for the severity of asthma, which along with the content of FeNO and eosinophils of blood allows to predict the response to treatment against IgE [7].

Identification of biomarkers can improve understanding of the phenotype of severe asthma. This progress in understanding the characteristics of the disease can lead to improved management of SA patients.

Given the new opportunities in prevention, diagnosis and treatment, the study of the epidemiology and clinical features of the course of severe asthma is an urgent task of modern medicine. The creation of the first Russian Severe Asthma Registry will serve to monitor and evaluate the efficacy, safety of prescribing therapy for patients with severe asthma, to isolate BA phenotypes and to unite regional specialists in the fight against this disease.

## **1.2. Rationale.**

The development of the Russian Severe Asthma Registry is aimed on supervising current problems that can be encountered when using separate registries for this nosology. Standardization of data collection will help to streamline interoperable sources of data on severe asthma across Russia, as well as to establish an accurate process for researchers to gain access to the Registry, which will collect data and use them in SA patient's management. Data on biomarkers such as FeNO, eosinophils, and IgE will be an important resource in the RSAR, helping to identify patients who are more likely to respond to biological agents.

An example of a successfully implemented observational study is the National Register of Patients with Idiopathic Pulmonary Fibrosis in the Russian Federation, a prospective observational study of idiopathic pulmonary fibrosis (IPF) in the Russian Federation, which was initiated in 2016 by the Russian Respiratory Society in conjunction with the Regional United Medical Informatization System. This innovative project was developed to study the features of epidemiology and the course of IPF, classified as rare diseases (ICD-10 code J84.1 - idiopathic pulmonary fibrosis) in the Russian Federation. It allows to obtain accurate epidemiological data on this nosology, to cooperate specialists from various specialties: pulmonologists, morphologists, radiation diagnostics specialists, and other experts at the federal and regional levels to improve the diagnosis and management of IPF. The Registry allows to achieve significant improvement in the physician's awareness about IPF and to reveal their interest in this problem. So, on the 01.09.2017, 185 doctors from 58 regions of the Russian Federation take part in the Registry, of which:

- 25 major freelance specialists-pulmonologists of the Ministry of Health of the Russian Federation;
- 57 scientists (professors, MD, PhD);

- 51 head of profile departments of state federal, regional and city health care institutions.

The registry improved the detection of IPF: currently there are 519 patients in, while there are total number of about 1000 IPF patients according to epidemiology in the Russian Federation. About 35% of patients in the IPF Registry are of working age. The functioning of the IPF Registry led to an improvement in the quality of medical care for patients with IPF. Within the framework of IPF Registry, 236 online consultations / opinions of federal or regional experts were conducted. During the work of the IPF Registry, the number of patients receiving specific antifibrotic therapy, which is the treatment of choice, has increased according to current recommendations: 97% of patients (59 of 61) receive nintedanib, registered in Russia with indication IPF. The IPF Registry is of high scientific and practical value and of great social significance for the diagnosis and treatment of this life-threatening disease.

The development of the Russian Severe Asthma Registry (RSAR) with a planned number of patients (CRFs) of 7,000 involving researchers from more than 30 cities has the potential to become an important Russian platform to research and a get a better understanding of the heterogeneity of the BA. the same as the rationale for proper use and monitoring the impact of BA treatment with new drugs.

## 2.0. OBJECTIVES

The RSAR objective is to develop a single automated system for monitoring the SA patient's management in Russia, to evaluate the efficacy and safety of pharmacotherapy prescriptions for patients with severe asthma, to determine the phenotypes of severe asthma, and to unite regional specialists in the fight against this disease.

### 2.1. Primary Objective(s)

The key objective of establishing the RSAR initiative is to:

- Percentage of patients with severe asthma according **frequency of exacerbations** (1, 2,  $\geq 3$  exacerbations) at the time of study enrollment;

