### 3.5. Inclusion Criteria

- Patients aged 12 years or older.  
Patients with confirmed diagnosis of severe asthma.
- Patients receiving treatment according to GINA step 5 or uncontrolled for 4 step. Uncontrolled patients are defined as having symptoms of severe asthma or frequent exacerbations.  
Signed informed consent.

---

 Severe symptoms of BA (Guideline of European Respiratory Society (ERS)/American Thoracic Society (ATS)) (2):

(a) BA with uncontrolled symptoms; ACT < 20, ACQ > 1,5;

(b) Limited air-flow rate, for example: FEV1 < 80 % of the norm (along with FEV1/FES at the lower limit of the norm or less) after wash-out period from the bronchodilators;

(c) Severe exacerbation and hospitalization, being in the ICU or on the mechanical ventilation of lungs over the past year.

 Frequent severe exacerbations of BA (guidelines ERS/ATS) (2):

Frequent severe exacerbations of BA (2 or more courses of systemic glucocorticoids over the past year).

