#### **4.4. Statistics analysis**

Primary and secondary statistical indicators will be presented using descriptive statistics methods. Qualitative variables will be presented in the form of incidence and percentage. The quantitative variables will be represented by numerical values, standard deviation indicators, minima and maxima, median and interquartile range. The frequency and severity of adverse events / reactions will be documented according to the Medical Dictionary of Regulatory Terminology, version 16.1. When analyzing the outcome of the disease among patients on therapy (drug), statistical analysis will be performed in a subgroup of newly identified patients. Evaluation of the outcome of SA can be determined by achieving a sufficient number of patients in a subgroup of newly identified patients and patients undergoing therapy (SA). The lack of comparison between groups of patients is due to the inaccuracy of these therapies in the history and treatment approaches.

In the course of the analysis, the standard statistical characteristics of morbidity, prevalence of the disease (SA) and their dependence on the basic demographic indicators (sex, age) will be assessed. The statistical analysis of the endpoints will be performed for patients with a diagnosis period of no more than 6 months from the date of inclusion in the register (a subgroup of newly identified patients) and also when the required amount of statistical data is collected within the register database.

The analysis will use standard methods of descriptive, frequency, logistic statistical analysis.

Hypotheses of the study. The main goal of the study is to obtain statistical estimates of the target epidemiological characteristics, formally asking questions about hypotheses of the study in this case is not applicable. After receiving the estimates, they are expected to be compared with similar ones, known in the foreign and domestic literature and official statistics.

Within the Registry, measures should be taken to collect data on the maximum number of patients within the claimed sample. In the absence of information within the fields of the individual registration card, the validating authority should separate information on the statuses "negative value", "no data", "not investigated".

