## 9. APPENDIX: Main variables

	Category	Variable's Fields Names	Response options (if applicable)
1	Inclusion Criteria	Is the patient suffering from uncontrolled asthma and taking medium-to-high doses of ICS?  Please check one of the following:  1. At the stage 5 GINA  2. (a) Uncontrolled in Stage 4: There are symptoms of severe asthma  2. (b) Uncontrolled in stage 4: there are exacerbations requiring OCS	No/Yes
2	Inclusion Criteria	The patient meets the criteria for the inclusion in RSAR	No/Yes
3	Detailed description of the patient	Visit date	DD / MM / YYYY
4	Detailed description of the patient	Date of Birth  Age at the moment of examination	DD / MM / YYYY  Full age (calculated automatically)
5	Detailed description of the patient	Gender	Male/female
6	Detailed description of the patient	Race	Caucasian / Southeast Asian / Northeast Asian / African / Mixed / Other
7	Detailed description of	IIIT	Decimal number (calculated automatically)

	the patient		
8	Detailed description of the patient	BMI	Decimal number (calculated automatically)
9	Detailed description of the patient	Height	Decimal number
10	Detailed description of the patient	Weight	Decimal number
11	Detailed description of the patient	Was the bronchial thermoplastics given to the patient?	No/Yes
12	Occupation	What is the current patient's occupation?	Free text entry
	Occupation	Occupational risks	- at the moment; - in anamnesis.
13	Anamnesis	What is current smoking status of a patient?	Never smoked / Former smoker / Currently smokers
14	Anamnesis	-Number of cigarettes smoked daily? (if marked "ex-smoker", "currently smokes")	Number
15	Anamnesis	-Years of smoking? (please indicate the period of time during which the patient smoked continuously)	Number
16	Anamnesis	-Pack-Years	Number (calculated automatically)
17	Anamnesis	-Years, passed after you quit smoking?  (please specify the time period from which the patient stopped smoking)	Number

18	Anamnesis	At what age did the symptoms of asthma start to appear in the patient?  Full years or months, if <1 year	Number
19	Anamnesis	Number of exacerbations requiring treatment with systemic glucocorticosteroids in the last 12 months?	Number
20	Anamnesis	The total number of episodes of invasive pulmonary ventilation?	Number
21	Anamnesis	Total number of ambulance calls due to asthma in the last 12 months?	Number
22	Anamnesis	Total number of hospitalizations due to asthma in the last 12 months?	Number

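### The primary exacerbation percentage at enrolment is partly set by the entry rule for step 4 patients, so it should be split by entry route before it is compared with outside sources

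*Combined protocol and SAP*

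**What the plan says.** Section 2.1 has one primary objective: the percentage of patients with 1, 2 or ≥3 "exacerbations) at the time of study enrollment". It defines neither the event nor the window, and lists no category for patients with none.

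Section 3.5 admits "Patients receiving treatment according to GINA step 5 or uncontrolled for 4 step". For step 4, "Uncontrolled patients are defined as having symptoms of severe asthma" (footnote 1) or frequent exacerbations (footnote 2). Footnote 1 lists (a) poor control on questionnaire scores, (b) airflow limitation, and (c) "Severe exacerbation and hospitalization, being in the ICU or on the mechanical ventilation of lungs over the past year". Footnote 2 reads "Frequent severe exacerbations of BA (2 or more courses of systemic glucocorticoids over the past year". Section 3.5 places no exacerbation requirement on step 5 patients.

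In the Section 9 appendix, the only exacerbation count is item 19: "Number of exacerbations requiring treatment with systemic glucocorticosteroids in the last 12 months". Item 1 records the entry route as step 5, step 4 with severe symptoms (2a) or step 4 with exacerbations needing oral steroids (2b), under the instruction "Please check one of the following". Option 2(b) carries neither the threshold of two nor the past-year window of footnote 2.

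Section 4.5 takes percentages over all patients in the analysed population, and Section 4.8 examines the primary endpoints for everyone in the registry. Section 4.4 says of the resulting estimates that "they are expected to be compared with similar ones, known in the foreign and domestic literature and official statistics". Subgroups are mentioned in Section 2.2 for the secondary objectives only, and entry route is not named.

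**The concern.** An outcome that also serves as an entry criterion is partly determined before any data are collected. Patients admitted on footnote 2 alone cannot have fewer than two qualifying steroid courses. Step 5 patients, and step 4 patients admitted on questionnaire scores or airflow limitation, may have any number, including none. The pooled distribution therefore mixes groups for whom the upper categories are free with a group for whom they are fixed.

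This does no harm if the figure is read only as a description of who was enrolled. The problem is the comparison planned in Section 4.4. A source that admits patients by another rule can give a different percentage even if the underlying disease burden is the same, and a pooled table does not let a reader see how much of a difference comes from the entry rule.

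**Working it through.** **The plan's own figure.** The plan gives no expected value for the primary percentage and no precision target. Its only related number is the recruitment target, which agrees with the yearly plan in Section 3.2: 2000 + 2000 + 1000 + 1000 + 1000 = 7000.

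**Does entry overlap with the endpoint?**

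| | Footnote 2 (Section 3.5) | Item 19 (appendix) |
|---|---|---|
| Event | course of systemic steroids for severe exacerbation | exacerbation treated with systemic steroids |
| Window | past year | last 12 months |
| Threshold | at least 2 | none (a count) |

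One counts courses and the other counts exacerbations, so they are not literally identical, but in substance they are the same event over the same window. Footnote 1(c) is a second past-year exacerbation criterion. It does not mention steroids or a count of two, so it does not by itself place a patient in the 2 or ≥3 categories.

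**What the overlap does to the pooled figure.** Let s be the share of the registry that qualifies solely through footnote 2, so would not have been enrolled without it. Let p be the share with ≥2 among everyone else. All of the first group have ≥2, so

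pooled share with ≥2 = s + (1 − s) × p,

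and the excess over p is s × (1 − p). The documents give neither s nor p, so both are assumptions:

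- p = 30%, s = 5%: 0.05 + 0.95 × 0.30 = 0.335, or 33.5%, an excess of 3.5 points.
- p = 30%, s = 20%: 0.20 + 0.80 × 0.30 = 0.44, or 44%, an excess of 14 points.
- p = 20%: 24% at s = 5% and 36% at s = 20%.
- p = 50%: 52.5% at s = 5% and 60% at s = 20%.

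**Against sampling error.** At n = 7,000 and a true share of 30%, the 95% half-width is 1.96 × √(0.30 × 0.70 / 7000) = 0.011, about 1.1 points. With p = 30%, even s = 5% moves the figure by more than that, and a larger sample does not reduce it.

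**Can the data as collected separate the routes?** Item 1 separates step 5 from step 4. Within step 4 it allows one tick, so a patient with both severe symptoms and frequent exacerbations is recorded under only one of them. Dividing step 4 by item 19 does not repair this. The part with item 19 ≥2 has 100% in the upper categories and the part below 2 has 0%, both by construction. The useful step 4 stratum is everyone meeting footnote 1(a) or 1(b), whatever their exacerbation count, and the one-tick format does not record it.

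**The case against.** The strongest reply is that this is a descriptive registry with no hypothesis test. Inclusion is sequential (Section 3.1), all eligible patients are to be included and screening logs are kept (Section 4.8), and the criteria are attributed to ERS/ATS guidance. The route mix is then meant to be that of the population the protocol defines, and the pooled percentage is a legitimate description of it. This stands. It does not cover the planned comparison with sources whose entry rules may differ; whether they do cannot be seen from the documents.

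It can also be said that the link from Section 2.1 to item 19 is inferred. That is true, and it is a reason to state the link. Option 2(b) has no threshold, so a patient recorded there could have a single exacerbation. That is also true, and it is why s is defined by footnote 2 and not by the ticked box.

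A reader might infer that recruitment mix alone could move the result by 28 points, from 44% to 72%, if the share on the exacerbation route went from 20% to 60% with p held at 30%. The documents do not support this. Patients who meet both criteria can be ticked either way, and moving them between boxes leaves the pooled figure unchanged. For example, start with 20% in 2(b) and 30% of the rest with ≥2: the pooled figure is 44%, and those others make up 0.80 × 0.30 = 24% of the registry. If all of them are step 4 and are re-ticked to 2(b), the route share becomes 44%, p becomes 0, and the pooled figure is still 44%. Holding p at 30% would give 0.44 + 0.56 × 0.30 = 0.608, about 61%. Only patients who would not have entered otherwise change the result.

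Nor does the plan make separation impossible. Step 5 against step 4 is recorded, and the symptom, spirometry and ACQ-6 fields help reconstruct the other criteria in part.

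**Conclusion.** The point holds as a limitation on interpretation with a cheap remedy. The primary percentage is partly set by the step 4 entry rule, and the plan would compare it with outside figures without showing how much. The size cannot be taken from the documents. With p assumed to be 30%, the excess is 3.5 points at s = 5% and 14 points at s = 20%; it is zero only if nobody enters solely through footnote 2 or if p is already 100%. The conclusion assumes that item 19 feeds the endpoint and that the items of footnote 1 are alternatives.

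Two stronger readings are tempting. One is that the pooled figure is invalid. It is not: it describes the enrolled cohort correctly. The other is that step 5 alone is the clean group for outside comparison, since Section 3.5 asks nothing of it on exacerbations. The documents do not clearly support that either: Section 3.4 describes both steps in terms of uncontrolled asthma, and the lead question of item 1 asks about uncontrolled asthma before offering the step 5 option. Using step 5 only would also leave out a main part of the target population.

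**What to change.** 1. In Section 2.1, state that the endpoint is item 19 over 12 months, and add a 0 category, since several routes admit patients with no exacerbation.
2. Make item 1 multi-select, recording footnotes 1(a), 1(b), 1(c) and 2 separately. Reconcile option 2(b) with footnote 2 on threshold and window.
3. Beside the pooled figure, report the distribution for step 5; for step 4 meeting footnote 1(a) or 1(b), whether or not they also meet an exacerbation criterion; and for step 4 qualifying only through exacerbations (footnote 1(c) or 2). For the last group, state what entry fixes: those meeting footnote 2 have at least two courses, and those there on 1(c) alone have fewer than two. Do not split step 4 on item 19, because that splits on the outcome.
4. For any outside comparison, give the source's entry rule and use the stratum that matches it.
5. Reconcile Sections 3.4 and 3.5 and item 1 on whether step 5 patients must be uncontrolled. Reconcile Section 4.4, which limits endpoint analysis to patients diagnosed within 6 months, with Section 4.8, which uses the whole registry.

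The cost is one eCRF format change and one extra table split, with no added patients or procedures. Uncertainty within each stratum will be wider than for the pooled figure. Records already entered under the one-tick format would directly support only the step 5 against step 4 split.
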